#### 4.4. Concomitant Medication

Subjects may receive medication that is clinically indicated, such as pain prophylaxis, as per the investigator's clinical judgement. The brand name (or, if unknown, the generic name), dose, dose unit (or dosage form if compound), frequency, route of administration, duration of use (start date

and, if applicable, stop date) and indication for all previous medications (taken 30 days prior to the date of the ICF signature) and concomitant medications (taken at the time of the ICF signature and during the course of the study) must be documented altogether in the concomitant medication record section of the case report form (CRF). Concomitant medications include intravenous fluids, herbal products, vitamins, and any over-the-counter medicines.

#### 4.5. Adjunctive Therapy/Procedure

An adjunctive therapy/procedure is defined as any procedure or intervention (e.g., psychotherapy, surgery, dental work, acupuncture, physiotherapy, chiropractic, osteopathy) used to treat an illness. Diagnostic tests or procedures (e.g., chest X-rays, ECG) are not considered as a therapy. These will not be recorded unless the test or procedure may have played a role in the occurrence of an adverse event or was performed to assess an adverse event.

The adjunctive therapy/procedure (type, duration of use [start date and, if applicable, stop date], and indication) received during 30 days prior to the date of the ICF signature and throughout the study must be recorded in the adjunctive therapy record of the CRF.

#### 4.6. Acceptable Contraceptive Regimens

Current regulations and guidelines pertaining to pharmaceutical industry require properly documenting and monitoring exposure to any drugs, whether investigational or not, under clinical research during pregnancy of study human subjects and/or their partner.

##### 4.6.1. Female Study Subjects

During the study, it is expected that females of childbearing potential will have to take appropriate measures to prevent pregnancy for 3 months after PDT, such as the use of medically acceptable contraceptive regimens namely:

- systemic contraceptives (e.g., transdermal patch, birth control pills, injectable or implantable or insertable hormonal birth control products);
- double-barrier method (e.g., diaphragm with intravaginal spermicide, cervical cap with intravaginal spermicide, condom with intravaginal spermicide, condom with diaphragm);  
or
- Intrauterine or intravaginal methods (e.g., vaginal contraceptive ring, intrauterine system with hormone release, copper intrauterine device).

Female subjects will be instructed to inform the investigator should a change in the contraceptive regimen occur during the study. Females of childbearing potential will be informed about this requirement in the ICF. Abstinence will not be considered as a medically acceptable contraceptive method.

Females who do not use an acceptable contraceptive regimen will be allowed to participate in this study only if they are not considered to be of childbearing potential: female who has had a hysterectomy, bilateral ovariectomy, or tubal ligation (performed during at least six months prior

to enrollment), is clinically diagnosed infertile, or is in a menopausal state (minimum of one year without menses). A female subject engaged with a vasectomized partner will not require an additional contraceptive method.

Should a case of pregnancy in female subject occur during the course of the study, the female subject will be monitored for the pregnancy outcome at birth, 6 months and 12 months following birth.

#### 4.6.2. Male Study Subjects

Contraceptive methods will be required for the male subject in the study as well as for the partner of the male subject in the study for 3 months after PDT. Contraceptive methods will not be required if the male subject in the study is vasectomized or if the partner of the male subject in the study is not considered to be of childbearing potential.

Cases of pregnancy in partner of male subject in the study will be monitored during the course of the study. Should a case of pregnancy in the partner of the male subject occur during the course of the study, the male subject will remain in the study and the partner of the male subject will be monitored for the pregnancy outcome (at birth, 6 months and 12 months following birth) after giving consent.

#### 4.7. Early Discontinuation Criteria

Early discontinuation from study will not, on its own, invalidate a subject for the safety analyses.

An investigator may choose to remove a subject from the study for any variety of reasons. Below is a list of possible reasons for removal of a subject; however, it does not include all possible justifiable reasons for removing a subject from the study.

1. The subject has been included in violation of the inclusion / exclusion criteria (as described under Section 4.3).
2. The subject chooses to discontinue participation for personal reasons (e.g., moving away, no time).
3. The subject chooses to discontinue, or is discontinued by the investigator or the sponsor due to intolerable, serious or unexpected adverse event or laboratory values judged to be clinically significant.
4. The investigator or the sponsor discontinues the subject for a significant protocol violation (e.g., pregnancy, current participation in another clinical study, etc.).
5. An illness newly develops as determined by the physician in charge that compromises continued participation.
6. The subject is uncooperative or does not comply with the protocol requirements (e.g., failure to return for scheduled visits at the enrolling study site, failure to complete study evaluation tools, failure to follow instructions).

7. In the investigator's or sponsor's judgment, withdrawal from the study would be in the subject's best interest (e.g., an immediate medical or surgical procedure is required that would compromise the subject's continued participation, lack of adequate therapeutic response resulting in intolerable symptoms or unacceptable risk).
8. The study is terminated by the sponsor.

For any subject who leaves the study, the investigator must complete the CRF up to the time study participation is terminated. Every effort should be made to ascertain the reason for discontinuation and to perform the early discontinuation procedures (Section 5.3.2). All reasonable effort must be made to contact subjects who fail to return for scheduled visits and to encourage them to comply with the procedure. All attempts to contact subjects must be clearly documented. The investigator will advise the sponsor immediately of every dropout by telephone, facsimile, or E-mail.

In case of withdrawal of consent, the date of and the reason for withdrawing consent will be collected. No additional data will be collected from the time of consent withdrawal.

---

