STUDY PROCEDURES: Eligible subjects will undergo screening evaluation conducted during the 30 days prior to enrollment. This phase will involve medical evaluation and eligibility assessment. Upon successful baseline evaluations, subject will be enrolled to receive PHO 2 mg/kg as a slow intravenous injection over 3 to 5 minutes. Forty to 50 hours after the injection, a laser light at a dose of 200 J/cm (630 nm wavelength) of diffuser length will be delivered to the tumor through navigational and or peripheral ultrasound guided bronchoscopy. Subjects will be hospitalized for 48-72 hours after PDT for safety monitoring. Ten to 15 days after PDT, all subjects will undergo surgery as per standard of care. Macroscopic and microscopic examinations of the tumor and surrounding healthy lung tissue will be evaluated to determine the effect of PDT on the tumor and the healthy/non-tumor lung tissue. Macroscopic examinations will be performed at the local institution. Microscopic examinations will be performed by a central reader. Follow-up assessments will include some or all the following procedures: physical exam; vital signs evaluation; body weight measurement; chest CT; chest X-ray; performance status; and clinical laboratory testing. All subjects will be asked general questions about the occurrence of adverse events, concurrent medical conditions, use of adjunctive therapy/procedure, and intake of concomitant medication.	
PLANNED STUDY ENROLLMENT DATES: Q2 2017 to Q1 2018.	
TEST PRODUCT, DOSE AND MODE OF ADMINISTRATION: Porfimer sodium (Photofrin®) 2.0 mg/kg delivered intravenously.	
DURATION OF TREATMENT: This study is a one-time administration of Photofrin® and one-time use of navigational with or without radial ultrasound bronchoscopy-PDT. Duration of Follow-Up: Subjects will be followed for 3 months post-surgery.	
MAIN CRITERIA FOR INCLUSION: 
 
1. Male or female subject is eighteen years of age and older (but less than 80 years of age).
 
2. Subject is diagnosed with primary or metastatic tumor < 5 cm located in peripheral lung that can be completely resectable (R0).
 
	

3. Subject is a candidate for surgical resection.
4. Subject is a candidate for bronchoscopy.
5. The tumor is accessible for unrestricted illumination of PDT.
6. Subject is deemed likely to survive for at least 3 months.

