***Surgery and post-surgery care***

1. Surgery and post-surgery care as per standard of care.
2. Reduced light settings and subject draping will be used to avoid potential problems from bright surgical lights:
  - from the moment the subject enters the hospital and will continue while the subject is in the surgical suite and on the surgical care units;

- surgery will be performed with room lights which are modified by amber filters that block wavelength below 550 nm;
- incisions will be shielded from inadvertent light exposure (e.g., sterile blue towels);
- remainder of the subject's skin will be draped in the usual surgical manner.

In addition, measuring oxygen saturation with pulse oximetry (pulse ox) will expose the skin to red light, which may cause skin burns if left in one place too long. Continuous monitoring can be carried out by setting up multiple monitors and rotating on and off status of the fixed sensors, or by moving a single sensor to different pulsating arteriolar bed, such as the finger, great toe, nose, or earlobe.

3. Record concomitant medications and adverse events.
4. Macroscopic and microscopic examinations of lung tumor tissue and lung healthy tissue. Lung tissue following surgical resection will be sent to the local pathology lab for macroscopic examination. Slides for microscopic examination will be prepared by the local pathology lab and sent to an independent expert pathologist (ARUP Laboratories, Salt Lake City, UT, USA) for central reading. The central assessor will interpret all histology samples obtained through surgery across all sites. Procedures for slide preparation and shipment will be performed as per laboratory instructions provided to participating sites.
5. Re-educate the subject on how to manage light exposure.

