## 8. ASSESSMENT OF SAFETY

Any adverse event/concurrent illness experienced by a subject during any portion of the study must be described in detail and be fully evaluated by the investigator. The investigator is responsible for recording and reporting all adverse events observed or reported during the study from informed consent signature until date of completion/discontinuation, regardless of drug-related assessment and/or clinical significance. Any pertinent information must be recorded in the Case Report Form (CRF) and additional comments describing the course and outcome of these events should be provided as appropriate.

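### Protocol 4.7 does not separate ending study procedures from ending follow-up, so removing a subject after the light session mainly cuts safety observation

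*Protocol*

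**What the plan says.** **Removal.** Protocol 4.7 opens its list with "An investigator may choose to remove a subject from the study for any variety of reasons". The reasons include "The subject has been included in violation of the inclusion / exclusion criteria" (reason 1), a subject who "is discontinued by the investigator or the sponsor due to intolerable, serious or unexpected adverse event" (part of reason 3), a newly developed illness (reason 5) and "The subject is uncooperative or does not comply with the protocol requirements" (reason 6). The section does not distinguish a subject who stops study procedures from one who leaves follow-up.

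**Data after removal.** Protocol 4.7 states: "For any subject who leaves the study, the investigator must complete the CRF up to the time study participation is terminated". Protocol section 8 has the investigator record AEs "observed or reported during the study from informed consent signature until date of completion/discontinuation". For discontinuation other than consent withdrawal, Protocol 5.3.2.2 asks for one evaluation: physical examination, vital signs, ECOG, laboratory tests, pregnancy test, medications and AEs. It lists no later contact, CT scan or tissue examination.

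**Treatment.** The synopsis says "This study is a one-time administration of Photofrin", with one light session. Protocol 3.2 places the injection on Day 1, the light on Day 3, surgery on Day 13-18 and the last visit on Day 103-108.

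**Tissue.** For operated subjects, "Lung tissue following surgical resection will be sent to the local pathology lab for macroscopic examination", and slides go to a central reader (Protocol, Surgery and post-surgery care). The surgery itself is standard of care.

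**Analysis.** The Safety Population is every enrolled subject who was injected (Protocol 10.5.1.2, SAP 5.2.2). Protocol 4.7 adds that early discontinuation alone does not take a subject out of the safety analyses.

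**The concern.** Safety is the primary objective, and the plan means to assess it up to 90 days after surgery (SAP 2.2). Once the light has been given, removing a subject cannot reduce exposure to drug or light. What it does change is whether anyone asks about AEs at the Day 20-25, 43-48 and 103-108 visits.

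The removed subject stays in the denominator. SAP 5.4.11.1 computes a percentage and an exact upper limit for each AE term, with no provision for shortened follow-up. A first event that nobody sees is therefore counted as no event, and the error can only lower the reported rate and its limit. Some removal reasons (an AE, a new illness) may themselves follow from the treatment, so subjects whose observation is cut need not be typical.

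Skin photosensitivity is the clearest case. It is an AE of special interest (Protocol 10.5.3, SAP 5.4.11.1), Protocol 7.1 says it may last 90 days or more, and the Light Challenge result is first recorded at the Day 43-48 visit. The secondary endpoint is exposed too: the planned operation may still take place after removal, but no text says that the specimen is then examined for the study.

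**Working it through.** **1. What continues after removal.**

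| Type of information | Provision | After removal |
|---|---|---|
| AEs at exit | Protocol 5.3.2.2 | One evaluation, every effort |
| Known AEs | Protocol 8.4.1 | Followed to resolution where possible |
| Known serious AEs | Protocol 8.5 | Followed until resolved or judged acceptable |
| New serious AEs | Protocol 8.4.3.1 | Taken if spontaneously reported within 90 days of injection |
| New non-serious AEs | None | Not actively sought |
| Specimen from later surgery | None | No route stated |

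The 90-day window from a Day 1 injection closes at about Day 91, which is 103 - 91 = 12 to 108 - 91 = 17 days before the scheduled last visit. Section 8.4.3.1 also words that window for subjects who discontinued study treatment. A subject removed after Day 3 has had all the treatment but has not completed the protocol, and so fits neither of its two categories clearly.

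**2. The plan's own figures.** Protocol 10.1 and SAP 3.1 use n = 10 and a one-sided 95% exact upper limit U, which solves P(X ≤ x | n, U) = 0.05. For x = 0 this is U = 1 - 0.05^(1/n). For x = 0 to 5 the results are 0.2589, 0.3942, 0.5069, 0.6066, 0.6965 and 0.7776. They match the printed 0.26, 0.39, 0.51, 0.61, 0.70 and 0.78.

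**3. One missed event.** If the missed event is the only one of its term, 1/10 (limit 0.39) is reported as 0/10 (limit 0.26).

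**4. Subjects actually observed.** The worked example concludes that with no events the true rate is below 0.27. Let m be the number of injected subjects removed before the event could be seen. The documents give no removal rate, so m = 1, 2, 3 is an assumption. The zero-event limit on the observed subjects is 1 - 0.05^(1/(10 - m)):

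| m | Observed | Upper limit |
|---|---|---|
| 0 | 0/10 | 0.259 |
| 1 | 0/9 | 0.283 |
| 2 | 0/8 | 0.312 |
| 3 | 0/7 | 0.348 |

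One such removal is enough to put the limit above 0.27.

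**5. Effect on the reported rate and limit.** Suppose the denominator stays at 10, none of the m subjects' events is seen, and removal is unrelated to risk. At a true rate of 0.27 the expected reported rate is 0.27 × (10 - m)/10, which is 0.243, 0.216 and 0.189 for m = 1, 2, 3. At a true rate of 0.26 the nominal 95% limit fails only when no event is seen, so its coverage is 1 - 0.74^(10 - m): 0.951 for m = 0, then 0.933, 0.910 and 0.878.

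**The case against.** A reader might infer more than the documents support.

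- **That removal never averts exposure.** Eligibility is re-checked before the Day 1 injection (Protocol 5.2.1.1), and the light follows 40-50 hours after it. Removal before either step can avert exposure. The point is confined to removal after the light session.
- **That every listed reason forces removal.** Section 4.7 says the investigator may choose to remove, and it asks for documented efforts to re-contact subjects who miss visits.
- **That AE collection stops altogether.** Only routine recording stops; the first four rows of the table above remain. A removal on Day 5 leaves (103 - 5)/103 to (108 - 5)/108, about 95%, of the period without scheduled contact. On the more generous reading of 8.4.3.1, spontaneously reported serious AEs are still taken for about 91 - 5 = 86 of those 98 to 103 days. Calling 95% unobserved is therefore too strong.
- **That the AE prompting removal is lost.** It is already recorded, and SAP 5.4.11.1 counts a subject once per preferred term, so a recurrence would add nothing. Understatement needs a different first event after removal.
- **That each removal before surgery costs 10% of the tissue data.** Only consent withdrawal bars further data. Nothing forbids examining the specimen; the route is simply unstated. Tissue taken before removal is kept.

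Two analysis points also weigh on the other side. SAP 5.4.1 tabulates and lists discontinuations with reasons and dates, so in a descriptive study of 10 a reader can see who was followed and for how long. And the general rule in SAP 5.1 divides by subjects with non-missing values, but nothing says when AE status counts as missing, so it does not supply a rule for cut-short follow-up.

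These points narrow the concern. They do not answer it for new non-serious events or for the specimen.

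**Conclusion.** The concern stands in a limited form. For an injected subject removed after the light session, the plan ends active enquiry about AEs while keeping the subject in the denominator, and what remains is passive or concerns events already known. The possible bias is downward and falls on the primary objective. Per removal, the illustration is 1/10 becoming 0/10 (limit 0.39 becoming 0.26), or 0/9 observed (0.283) against the claimed bound of 0.27.

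These are consequences per removal, not forecasts. They rest on an assumed number of removals, on the unseen event being a first event of its term in that subject, and, for the step from 1/10 to 0/10, on its being the only one among the ten. If nobody is removed, the plan's table stands as printed.

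**What to change.** Amend Protocol 4.7 and section 8 so that an injected subject who is discontinued for any reason other than consent withdrawal or study termination:

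- stays in AE follow-up at the Day 20-25, 43-48 and 103-108 contacts, by telephone if needed and as far as the subject agrees;
- has AEs recorded to Day 103-108;
- has any resected specimen sent for the planned local macroscopic and central microscopic examination.

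Reconcile the end of AE recording in section 8 with 8.4.1, 8.4.3.1 and 8.5, including which window in 8.4.3.1 applies to a subject who has finished treatment but not the protocol.

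The change concerns data collection only. It sets no rule on whether injection, light treatment or surgery goes ahead, and it cannot bind subjects who choose to leave or who do not return. The cost is an amendment of a few sentences and some site effort for the few subjects who are hard to follow.

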## 5. STUDY PROCEDURES

A detailed description of the time and events schedule of planned study assessments and visit procedures is outlined in Appendix 13-1.

### 5.1. Pretreatment Procedures

Pretreatment procedures (ICF and screening) will be performed during 30 days prior to enrollment. All procedures performed to confirm the primary diagnosis must be performed no more than 60 days prior to ICF signature.

#### 5.1.1. Informed Consent

Before a subject is enrolled in this study and prior to any evaluation performed for the study, the investigator or designee must explain the study to the subject in sufficient detail to allow for her/his informed decision to participate. Availability of alternative treatment must be fully explained to the subjects and documented in the Patient Information Sheet (PIS)/Informed Consent Form (ICF). If the subject understands the requirements of the study and agrees to participate, the subject will sign the ICF. This form must also be signed by the investigator or designee. All signatures must be dated. If the investigator chooses to alter a medical regimen of the subject for the purpose of enrolling the subject in this study, the informed consent for the study should be signed at that time and prior to any alteration in the subject's ongoing therapeutic regimen. A copy of the signed and dated consent form must be given to the subject before the start of the study. The signed ICF must be available for the sponsor monitor or designee for on-site review. Upon willingness and meeting requirements to participate in the study, each subject will be enrolled in the study by assignment of a unique sequential enrollment number for each study site.

#### 5.1.2. Screening Procedures

Before any study-specific procedures are performed, informed consent will be obtained (Section 5.1.1). All subjects will undergo the following evaluations at the screening visit:

1. Review of eligibility criteria (including primary diagnosis);
2. Collection of demographic data;
3. Collection of medical and oncological history, including concurrent medical conditions;
4. Comprehensive physical examination as per SoC (excluding genital/gynecologic and urogenital unless indicated);
5. ECOG Performance Status (Appendix 13-2);
6. Skin phototype according to Fitzpatrick Classification (Appendix 13-3);
7. Vital signs (pulse, blood pressure, temperature, and respiration rate), body weight (SoC), and height assessment;
8. Chest X-ray if has not been performed up to 90 days prior to ICF signature;

9. A 5-minute resting 12-lead ECG if has not been performed up to 30 days prior to ICF signature;
10. Clinical laboratory (Appendix 13-4);
11. Serum  $\beta$ -HCG (only for female subjects of childbearing potential);
12. Collection of all adjunctive therapies/procedures and medication information including over-the-counter and phytomedicinal products currently taken by the subject as well as up to 30 days prior to the date of the ICF signature;
13. Collection of adverse events.

